TEAE Treatment Emergent Adverse Event

UCI Upper Confidence Interval

ULOQ Upper Limit of Quantification

3 Modification History

Unique Identifier for Version	Date of IAP Version	Author	Changes from the Previous Version
Final 1.0	12-Oct-2020		n.a.

4 Purpose of the Integrated Analysis Plan

The purpose of this IAP is to document technical and detailed specifications for the final analysis of data collected for protocol MS700568-0031. Results of the analyses described in this IAP will be included in the Clinical Study Report (CSR). Additionally, the planned analyses identified in this IAP will be included in regulatory submissions or future manuscripts. Any post-hoc, or unplanned analyses performed to provide results for inclusion in the CSR but not identified in this prospective IAP will be clearly identified in the CSR.

The IAP is based upon section 9 (Statistical Considerations) of the trial protocol and protocol amendments and is prepared in compliance with ICH E9.

5 Objectives and Endpoints

Objectives	Endpoints (Outcome Measures)	IAP Section
Primary		
To examine the effect of repeat-dose cladribine 10 mg tablets on the repeat-dose pharmacokinetics of the monophasic oral contraceptive Microgynon by assessment of its constituents, ethinyl estradiol (EE; 30 µg/tablet) and levonorgestrel (LNG; 150 µg/tablet)	 Primary PK parameters calculated for EE and LNG from plasma concentrations: Area under the concentration—time curve from zero to tau at steady state (AUCτ,ss), and the maximum plasma concentration at steady state (Cmax,ss). Secondary PK parameters calculated for EE and LNG: Cmin,ss; Ctrough; tmax,ss; Cave,ss; and peak-to-trough fluctuation (PTF%). 	16.1
Secondary		
To examine the safety and tolerability of Microgynon and cladribine co-administration.	Occurrence of treatment-emergent adverse events (TEAEs), changes in safety laboratory tests, 12-lead electrocardiograms (ECGs) (morphology, and time intervals [PR, QRS, RR, QT and corrected QT intervals [QTc]), and vital signs (PR, SBP, DBP, body temperature)	15
To examine cladribine exposure	Cladribine C _{max} and t _{max}	16.1

ss=at steady state; AUC_T=Area under the concentration-time curve from zero to tau; C_{av}=average concentration; C_{min}=minimum observed concentration during a complete dosing interval; C_{trough}=concentration observed immediately before next dosing; DBP=diastolic blood pressure; ECG=electrocardiogram; EE=ethinyl estradiol; h=hour; LNG=levonorgestrel; CGI PK=pharmacokinetic; PTF%=peak-to-trough fluctuation; PR=pulse rate; QTc=corrected QT intervals; SBP=systolic blood pressure; t_{max}=time to reach the maximum observed concentration collected during a dosing interval; TEAEs=treatment-emergent adverse events.

6 Overview of Planned Analyses

All final, planned analyses identified in the Clinical Trial Protocol and in this IAP will be performed only after the last subject has completed the last visit, i.e. end of trial visit/early termination visit with all trial data in-house, all data queries resolved, and the database locked.

A blinded data review meeting will be held prior to database lock. In addition, no database can be locked until this IAP has been approved.

7 Changes to the Planned Analyses in the Clinical Trial Protocol

The statistical methods as described in the protocol were adopted.

8 Protocol Deviations and Analysis Sets

8.1 Definition of Protocol Deviations and Analysis Sets

Important protocol deviations are protocol deviations that might significantly affect the completeness, accuracy, and/or reliability of the study data or that might significantly affect a subject's rights, safety, or well-being.

The following deviations will be identified and confirmed prior to or at the Data Review Meeting at the latest.

Important protocol deviations include but are not limited to

- Deviations from the inclusion and exclusion criteria
- Concomitant medication violations (see Section 6.5.2 of the protocol)
- Use of prohibited medicines (see Section 6.5.3 of the protocol)
- Subjects that receive incorrect treatment or dose
- Sample processing errors that may lead to inaccurate bioanalytical results
- Deviation from Good Clinical Practice
- Non-compliance to study procedures or deviations from study procedures likely to affect the primary endpoints (e.g. subject develops withdrawal criteria whilst on the study but is not withdrawn)

In addition, for the definition of the PK analysis set (see section 8.2) events likely to affect the comparability between treatments of PK results will be identified. Important events to be considered are:

- Vomiting or diarrhea following oral dosing (these instances will be discussed on a caseby-case basis)
- Deviation from study medication compliance in terms of medical conditions and/or AEs that may have interfered with drug disposition or with respect to factors likely to affect the primary endpoints

All important protocol deviations will be documented in Clinical Data Interchange standard consortium (CDISC) Study Data Tabulation Model (SDTM) dataset whether identified through sites monitoring, medical review or programming.

In addition, pre-dose/trough samples which have been taken after the subsequent dosing will be reported as protocol deviation. The resulting concentrations will be included in concentration listings but excluded from descriptive statistics of trough concentrations.

8.2 Definition of Analysis Sets and Subgroups

The analysis populations are specified below. The final decision to exclude participants from any analysis population will be made during a blinded data review meeting prior to database lock and unblinding.

It is important to note that only Days 9 to 13 cladribine and placebo treatments are serving the purpose of the primary and secondary study objectives (ie, examining placebo-controlled cladribine effects on the PK and of the active Microgynon components EE and LNG), while Days 15 to 19 cladribine and placebo treatments are only factored into the study design to allow for a timely initiation of the second 5-day cladribine treatment for participants assigned to the treatments sequence cladribine-placebo, in a blinded fashion.

Table 1 Analysis Populations

Analysis Set	Description
Screening	The Screening Analysis Set will include all participants who provided signed informed consent, regardless of enrollment (start of run-in-period) or randomization or treatment status in the study.
Enrolled	All participants who start the run-in-period
Safety	The Safety Analysis Set will include all participants who receive at least 1 dose of study intervention. Participants will be analyzed according to the actual treatment they
	receive.
Pharmacokinetic	The evaluation of PK data will be based on the PK Analysis Set, a subset of the Safety Analysis Set, which is characterized by the following criteria:
	The completion of both periods;
	Participants must be 100% compliant to cladribine and placebo;
	Absences from 100% compliance taking Microgynon

Analysis Set	Description
	considered as significant by the investigator and/or by the attendees during data review meeting;
	The availability of all 4 primary endpoints;
	The absence of any important protocol deviation or events, which would render the data incomparable between treatments. Reasons to exclude a participant are events such as nonconformance during study intervention, vomiting and diarrhea or any other reason which could render the plasma concentration-time profile unreliable. In exceptional cases, the use of concomitant medication could be a reason for excluding a participant.
	Participants will be analyzed according to the actual treatment they receive.

; PK=pharmacokinetic;

9 General Specifications for Data Analyses

Statistical analyses will be performed using the computer program package SAS® System for WindowsTM (Version 9.4 or later; SAS Institute, Cary, North Carolina, USA).

The results of this trial will be reported using summary tables, figures, and data listings, as appropriate. All data will be summarized by treatment sequence, period, treatment and/or scheduled time point, as appropriate.

For demographic, baseline and safety assessments, continuous measurements will be summarized by means of descriptive statistics (ie, number and percentage of observations, number and percentage of missing observations, mean, standard deviation [SD], median, 25th and 75th percentiles [Q1 and Q3], minimum, and maximum) and categorical data will be summarized by means of frequency tables (ie, count and percentages), if not stated otherwise. Mean, Median, Q1, Q3, Min, Max will have the same precision as the SDTM data (decimal places). SD will be presented with one decimal place more than the mean. For subject disposition and demographic tables, the denominator will be the number of subjects in the analysis set. Counts of missing observations will be included as a separate category.

If not otherwise specified, 'baseline' refers to the last scheduled measurement before administration of cladribine or placebo on Day 9 of each period.

However, if a subject is missing the baseline collection, the previous non-missing evaluation could become the baseline value. If no baseline or previous to baseline evaluations exist, then the baseline value will be treated as missing.

The following calculations and derivations, as applicable, will be used:

- Change from baseline: post-baseline visit value baseline value
- Duration of AE (in days hh:mm) = end date and time start date and time of the AE, if
 missing time for either the beginning or end then = end date start date + 1; in case of
 multiple records for the same AE, the duration will be calculated over all these records
- Days hh:mm from last dosing of cladribine/placebo or microgynon = start date and time of the event date and time of dose administration; (for treatment- emergent AEs), if missing time for either the dosing or event then = event start date date of dose administration + 1
- Rel. Day in study = start date of the event or measurement date of first admin of microgynon + 1 (for events or measurements on or after the day of dosing)
- Rel. Day in study = start date of the event or measurement date of first admin of microgynon (for events or measurements before the day of dosing)

Object No. Global Version ID:

• Rel. Day in period = start date of the event or measurement – date of first admin + 1 of microgynon within run-in period, period 1 or period 2 (for events or measurements on or after the day of dosing)

Repeated laboratory assessments will be flagged as repeats in the subject data listings and not included in summary tables statistics (unless the scheduled measurement was considered unreliable, e.g. due to technical reasons, and needed to be replaced by an unscheduled repeat measurement).

In this phase 1 PK study missing observations will be assumed to be missing completely at random (MCAR). No action will be taken to handle missing data. A subject who withdraws prior to the last planned observation in a trial period will be included in the analyses up to the time of discontinuation.

10 Trial Subjects

The subsections in this section include specifications for reporting subject disposition and treatment/trial discontinuations. Additionally, procedures for reporting protocol deviations are provided.

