Participants who withdraw from the study for any reason or do not have a full PK dataset will not routinely be replaced. If the assumed drop-out rate of 18 % to 30% will be unexpectedly higher, a discussion should occur between the Investigator and the Sponsor regarding whether a replacement may be considered. The number of participants evaluable for BE (16 participants) need to be maintained. Each replacer will be assigned to the treatment sequence of the replaced participant. Details on this procedure are described in the Operations Manual.

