All statistical analyses and descriptive summaries of pharmacokinetic data will be performed on the PK Analysis Set. All available concentration/PK data will be listed. Data of subjects not in the PK analysis set or invalid data will be flagged accordingly; a reason for exclusion will be detailed in the CSR (e.g. a footnote or a table of exclusions). Any flags should be included in the study specific ADaM data sets.

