16.1.2 Secondary Pharmacokinetic Endpoints

Secondary PK parameters calculated for EE and LNG: $C_{min,ss}$; C_{trough} ; $t_{max,ss}$; $C_{av,ss}$; and peak-to-trough fluctuation (PTF%). Secondary PK parameters calculated for Cladribine: C_{max} and t_{max} .

Secondary parameters will be listed.

Summary statistics will be provided for all secondary PK parameters for EE, LNG and cladribine in plasma by analyte, treatment and day, if applicable.

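### Cladribine Cmax and tmax are summarised only in women who qualify for the EE/LNG comparison, so a full cladribine profile from a woman who later withdraws enters no summary

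*SAP*

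**What the plan says.** Cladribine exposure is a listed secondary objective, with Cmax and tmax as its endpoint (Protocol Section 3, Table 1; SAP Section 5). SAP Section 16.1.2 repeats this under "Secondary PK parameters calculated for Cladribine" and plans summary statistics by analyte, treatment and day.

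The population is set in SAP Section 16.1: "All statistical analyses and descriptive summaries of pharmacokinetic data will be performed on the PK Analysis Set". SAP Section 8.2 defines that set. Its criteria include "The completion of both periods" and "The availability of all 4 primary endpoints", the four endpoints being AUC and Cmax at steady state for EE and for LNG. They also include full compliance with cladribine and placebo, and the absence of events such as vomiting or diarrhea that make a profile unreliable. No separate set is defined for cladribine.

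SAP Section 16.1 also provides that all available PK data are listed, that data from women outside the set are flagged, and that the CSR gives the reason for exclusion.

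SAP Section 9 carries a general sentence on withdrawals: such a woman "will be included in the analyses up to the time of discontinuation". It names no analysis set.

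Protocol Section 7.2 gives the planning figures: 16 participants evaluable for bioequivalence and an assumed drop-out rate of 18% to 30%.

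**The concern.** The entry criteria for the only PK set were written for a within-woman comparison. A Test/Reference ratio for EE or LNG needs both periods and the EE/LNG profiles. Cladribine Cmax and tmax need neither: they come from samples on Days 10 to 13 of the one period in which cladribine is given on Days 9 to 13.

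A woman randomised to cladribine-placebo who withdraws after Day 13 of Period 1 has therefore supplied everything the cladribine endpoint asks for, and is still left out of its summary. She remains in the safety tables under Microgynon + Cladribine, because those use the Safety Analysis Set. Cladribine exposure and cladribine safety are then summarised on different women. What is at stake is some precision and completeness in a descriptive secondary summary, in a small trial where each profile counts.

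**Working it through.** **Step 1. Set each criterion against what each endpoint needs.**

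- Completion of both periods: needed for the paired EE/LNG ratio; not needed for cladribine Cmax/tmax.
- All four EE/LNG primary endpoints: needed for the four-interval bioequivalence rule; not needed for cladribine.
- All cladribine doses taken: relevant to both.
- All placebo doses taken: relevant to the comparison; not to cladribine exposure.
- No vomiting, diarrhea or similar event: relevant to both, but for cladribine only in the cladribine period.

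Cladribine sampling (Protocol Section 8.5) is predose on Day 9, then predose and 0.25, 0.5, 1, 1.5 and 2 h postdose on Days 10 to 13. It is complete 2 h after the Day 13 dose, before the main EE/LNG profile on Days 14/15.

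**Step 2. How many women could be affected.** The plan's figure of 16 cannot be reproduced: the total sample size is redacted and no CV, assumed ratio or power is visible. I take 16 as given and assume that drop-out is counted from randomisation, which Protocol Section 7.2 does not state.

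- N = 16 / (1 − d)
- d = 0.18: 16 / 0.82 = 19.5, so 20 women and 20 − 16 = 4 drop-outs
- d = 0.30: 16 / 0.70 = 22.9, so 23 women and 23 − 16 = 7 drop-outs (24 and 8 if N is made even for 1:1 allocation)

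The documents do not give the timing of drop-out. If all drop-outs leave between periods and split evenly by sequence, only the cladribine-placebo half has a full profile: 4 × 0.5 = 2 up to 7 × 0.5 = 3.5 (8 × 0.5 = 4). If half leave between periods and the rest leave before Day 13 of Period 1, the count is 1 to 1.75 (2). If all leave before Day 13 of Period 1, it is 0. A working range is k = 0 to 4. Without the even-split assumption it could in principle reach all 7 (8).

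**Step 3. Effect on the cladribine summary.** With a common SD on the log scale, the SE of the mean log Cmax is proportional to 1/√n. Going from 16 to 16 + k women reduces it by 1 − √(16 / (16 + k)):

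- k = 0: 0%
- k = 1: 1 − √(16/17) = 3.0%
- k = 2: 1 − √(16/18) = 5.7%
- k = 3: 1 − √(16/19) = 8.2%
- k = 4: 1 − √(16/20) = 10.6%

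This ignores the mix of one- and two-tablet daily doses (Protocol Table 3), which also drives the spread of Cmax.

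**Step 4. Effect on the primary analysis.** The ANOVA has subject within sequence as a fixed effect. A woman with one period adds one observation and one parameter, so she is fitted exactly and contributes nothing to the treatment contrast. Residual df are 32 − 16 − 1 − 1 = 14 with 16 completers, and 38 − 22 − 1 − 1 = 14 with six one-period women added. Fitting both to simulated data gave the same log-scale estimate (0.0549), SE (0.0605) and 90% CI (−0.0517 to 0.1615).

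**The case against.** **The plan has one clear rule.** A reader might infer that SAP Sections 9 and 16.1 contradict each other, one keeping withdrawn women and the other dropping them. The documents do not support that. Section 9 holds general specifications, and Section 16.1 is the specific rule for PK. The general sentence can be read as applying within whichever set is in force, and it has a natural use in safety. This objection stands: the Section 9 wording is loose, not contradictory.

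**The set has a purpose.** Protocol Section 8.5 and SAP Section 16.1.4 say cladribine is sampled only to confirm exposure. If the question is whether the women behind the EE/LNG ratios were exposed, the PK Analysis Set is the right population. This stands as a reason to keep that summary. It does not justify having no other, since cladribine exposure is also a secondary objective in its own right.

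**Nothing is hidden.** It would be wrong to say the profiles are ignored, because they are listed and flagged with reasons. That stands. They are missing only from the summaries.

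**A looser set could let in poor data.** Protocol Section 6.4 makes full compliance with cladribine and placebo a condition of PK evaluation, and Table 7 excludes vomiting and diarrhea cases. A cladribine set that did not restate the relevant safeguards would be worse than the present one. This stands and shapes the fix.

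**Conclusion.** The point holds as a cheap improvement to a secondary descriptive summary, not as an error in the plan. The PK Analysis Set applies two criteria to cladribine Cmax/tmax that have nothing to do with them, and a full profile from a woman who leaves after her cladribine period can be left out as a result.

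The size is small and uncertain: perhaps 0 to 4 profiles beyond the 16, and a 0% to 11% smaller standard error. This assumes 16 evaluable women, drop-out counted from randomisation, an even split by sequence and a common SD.

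Three stronger readings are tempting and not supported:

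- That 18% to 30% of women lose a complete cladribine profile. That range is total drop-out. Women who leave before Day 13 of Period 1, and placebo-cladribine women who leave before their own cladribine course, have no full profile to lose.
- That the summary is biased towards women who tolerated treatment. The documents give no link between cladribine Cmax within 2 h of a supervised dose and later withdrawal, and the SAP assumes data are missing completely at random.
- That the bioequivalence conclusion is affected. Step 4 shows it is not.

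One detail remains open: completion of both periods is not tied to a day, so a woman who withdraws late in Period 2, after the Day 15 sample, might still qualify.

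**What to change.** In SAP Sections 8.2 and 16.1:

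- Define a cladribine PK set: women in the Safety Analysis Set who took all planned Day 9 to 13 cladribine doses, have evaluable cladribine samples, and had no vomiting, diarrhea or other event making that profile unreliable, whether or not they completed both periods. State what counts as evaluable.
- Summarise cladribine Cmax, tmax, Cpre and concentrations on this set, and also on the PK Analysis Set, so that exposure is still confirmed in the women behind the EE/LNG ratios.
- Keep the PK Analysis Set for all EE/LNG analyses.
- In SAP Section 9, say that the withdrawal sentence applies within each analysis set.
- In SAP Section 7, which now reports no change from the protocol, record the departure from Protocol Table 7 and from the cladribine-and-placebo compliance condition in Protocol Section 6.4.

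The cost is a few sentences, one extra population flag, a second run of the cladribine tables, and a footnote explaining why n differs between cladribine and EE/LNG. The change should be made before database lock.

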10.1 Disposition of Subjects and Discontinuations

This following will be presented in a summary table:

- Total number of subjects screened (ie, subjects who gave informed consent)
- Total number of subjects enrolled
- Total number of subjects randomized
- Number of screened subjects who discontinued from the trial prior to treatment overall and grouped by the main reason for discontinuation:
 - Subject did not meet all eligibility criteria
 - Withdrew consent
 - o Other (COVID-19-related and COVID-19-non-related)
- Number of treated subjects overall
- Number and percentage of treated subjects who completed study
- Number and percentage of treated subjects who discontinued the study, with the primary reason of discontinuation:
 - Adverse event

Document No.

Object No.

Global Version ID:

- Lost to follow-up
- Protocol non-compliance
- Death
- Withdrew consent
- o Other (COVID-19-related and COVID-19-non-related)
- Number and percentage of treated subjects who completed microgynon treatment
- Number and percentage of subjects who discontinued microgynon treatment with the primary reason of discontinuation
- Number and percentage of treated subjects who completed MS treatment

Number and percentage of subjects who discontinued MS treatment with the primary reason of discontinuation.

A listing of discontinued subjects will be provided.

A listing of participants affected by the COVID-19 related study disruption by unique subject number identifier will also be provided.

10.2 Protocol Deviations

10.2.1 Important Protocol Deviations

Listings of important protocol deviations will be provided including the date and relative day in relation to dosing in the relevant period.

10.2.2 Reasons Leading to the Exclusion from an Analysis Set

All criteria/reasons leading to the exclusion of a subject from an analysis set will be listed based on the safety set.

Reasons for excluding individual PK concentrations will also be listed separately and flagged in the main listing based on the safety analysis set.

Any PK concentrations and/or PK parameters excluded from PK analysis set or summary statistics will be included in subject listings and flagged; a reason for exclusion will be detailed in the CSR (e.g. a footnote or a table of exclusions). Any flags should be included in the study specific ADaM data sets.

Object No.

Global Version ID:

11 Demographics and Other Baseline Characteristics

